Studies of tamoxifen in the adjuvant and preventive setting have demonstrated that a decline in MD of approximately 10% is consistently associated with better outcomes . In a case-control analysis nested within the IBIS-I breast cancer prevention trial, Cuzick *et al.*, observed that approximately 46% of tamoxifen-treated women experienced a  $\geq 10\%$  reduction in MD at 12–18 months and these women had a 63% reduction in breast cancer risk (odds ratio [OR] =0.37, 95% confidence interval [CI] =0.20–0.69,  $p=0.002$ ) as compared with all women on placebo (regardless of MD) . In contrast, tamoxifen-treated women with  $<10\%$  reduction in MD did not experience risk reduction compared to all women on placebo (OR=1.13, 95% CI 0.72–1.77,  $p=0.60$ ). Further, several other retrospective analyses have reported that among women with ER-positive breast cancer treated with tamoxifen, those whose MD declined in the unaffected breast , had better outcomes (reduced risk of recurrence  or death from breast cancer ). In contrast, other agents that have shown chemopreventive efficacy, including raloxifene and exemestane, have not been reported to consistently reduce MD .

The original corporate sponsor completed a 6-month study of 4-OHT gel for breast density reduction using 0.05% (w/v) 4-OHT, a less concentrated gel than currently available (0.2% (w/v) gel). Though overall results of this study were nonsignificant, post-hoc analysis of patients with baseline breast density  $\geq 80\%$  ( $n=19$ ; 4-OHT=9; placebo=10) revealed a  $-4\%$  vs. a  $+0.7\%$  ( $p=0.024$ ) change in baseline density following 6 months of treatment for 4-OHT gel 1mg/d per breast vs. placebo, respectively (source NCI TORF FF-2015 document).

Taken together, changes in MD would be an ideal “biomarker” to be evaluated as the primary endpoint in this short-term prevention using 4-OHT gel in high risk women. The duration of 12 months was chosen because most studies referenced above reported mammographic data at least 12 months.

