#### 4. PARTICIPANT SELECTION

##### 4.1 Inclusion Criteria

- 4.1.1 Women age 40-69 years, or less than 40 years if 5-year breast cancer Gail risk is  $\geq 1.66\%$ .
- 4.1.2 Mammographically dense breast (heterogeneously dense (C) or extremely dense (D), based on ACR BIRADS© fifth edition classification or heterogeneously dense (3) or extremely dense (4), based on ACR BIRADS© fourth edition classification) in either breast.
- 4.1.3 ECOG performance status  $\leq 1$  (Karnofsky  $\geq 70\%$ ; see Appendix A)
- 4.1.4 Participants must have normal organ and marrow function defined as ALL of the below:
  - White Blood Cells  $\geq 3,000/\text{microliter}$
  - Platelets  $\geq 100,000/\text{microliter}$
  - Total bilirubin  $\leq 1.5 \times \text{institutional upper limit of normal (ULN)}$
  - AST (SGOT)/ALT (SGPT)  $\leq 1.5 \times \text{institutional upper limit of normal (ULN)}$
- 4.1.5 Participant must have a gynecology examination within the last 5 years (gynecology examination is not required if participant had a hysterectomy).
- 4.1.6 Premenopausal women using a hormonal or non-hormonal Intra-Uterine Device (IUD) birth control method will be eligible, if they have been on the same IUD for at least 3 months prior to enrollment and plan to continue using the same method throughout the study.
- 4.1.7 Women who are using postmenopausal hormones, and are planning to continue the same regimen through the study intervention are eligible to participate.
- 4.1.8 Willingness to avoid exposing breast skin to natural or artificial sunlight (i.e. tanning beds) for the duration of the study.
- 4.1.9 Ability to understand and the willingness to sign a written informed consent document.

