##### 4.2 Exclusion Criteria

- 4.2.1 History of allergic reactions attributed to compounds of similar chemical or biologic composition to 4-OHT gel.
- 4.2.2 Uncontrolled intercurrent illness including, but not limited to, ongoing or active infection, symptomatic congestive heart failure, unstable angina pectoris, cardiac arrhythmia, thromboembolic disease, or psychiatric illness/social situations that would limit compliance with study requirements.
- 4.2.3 Pregnant, unwilling to use adequate contraception during study treatment duration, had given birth, or nursed at any time during the last 12 months (see footnote 1 below).

- 4.2.4 Women with a previous history of invasive breast cancer or bilateral DCIS or current untreated DCIS. Women with a history of cancer within the last 3 years, except for non-melanoma skin cancer. Women with unilateral DCIS (with or without radiation therapy) are eligible as long as they have an unaffected breast.
- 4.2.5 Prior bilateral breast surgery (mastectomy, segmental mastectomy, or breast augmentation surgery including breast implants or breast reductions).
- 4.2.6 Women with “mosaic mammographic screening views”, i.e., whose larger breast size precludes being imaged within a single mammographic screening view.
- 4.2.7 Women with active liver disease.
- 4.2.8 Women with a uterus and abnormal uterine bleeding, or prior diagnosis of endometrial hyperplasia, endometrial polyps, or endometrial cancer.
- 4.2.9 Prior use of SERMS and AIs, except for a maximum of 3 months and at least 12 months prior.
- 4.2.10 Skin lesions on the breast that disrupt the stratum corneum (e.g., eczema, ulceration).
- 4.2.11 Treatment with any investigational drug or investigational biologic within 30 days of initiating study treatment or during the study.

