## 8. CRITERIA FOR EVALUATION AND ENDPOINT DEFINITION

### 8.1 Primary Endpoint

The primary objective of this study is to evaluate mammographic density (MD) changes induced by 4-OHT gel versus placebo in women with mammographically dense breast. Our hypothesis is that 4-OHT will reduce MD. Baseline and 12 months mammogram [or mammograms from Month 13-18 under the COVID-19 contingency plan] will be evaluated for 4-OHT effect using Cumulus software for the primary endpoint evaluation. Analysis will be based on tomosynthesis imaging using the 2D synthetic image.

MD will be classified using BIRADS descriptions on mammographic reports (i.e: predominantly adipose tissue, scattered fibroglandular densities, heterogeneously dense or extremely dense). BIRADS MD assessment is a consistently utilized measure of breast fibroglandular tissue volume, which can be universally followed and reproduced. BIRADS is a scheme for putting the findings from mammogram screening into a small number of well-defined categories. In addition to BIRADS, baseline and follow up MD will be quantified and recorded using semi-automated software, Cumulus, which has been utilized in earlier density assessment studies. Cumulus reading will be centralized with the reader blinded to the timepoint and treatment group.

For the primary endpoint, the densest breast will be used.

At each institution mammographic images will be collected by a study specific data coordinator who will be overseen by the site Investigator. This data coordinator will also ensure that images are collected in usable format with appropriate de-identification. Follow the instructions in Section 10.2 for Collection and Handling of images.

In summary, the effect of utilized software on the density percent assessment is estimated to be minimal. Based on this, we will use:

- a) Downgrading of the baseline reported BIRADS breast density.
- b) Decrease in breast fibroglandular density by 10% or more as assessed by semi- and automated Breast Density software.

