#### **13.1 Study Design/Description**

A total of 198 potentially eligible participants will be consented and screened for eligibility and, with a conservative estimate, 158 (80%) participants are expected to be eligible. These 158 women will be randomized 1:1 into one of two groups: placebo or 4-OHT gel 2 mg per breast. Treatment will last for 52 weeks. Considering an attrition rate of approximately 19%, we expect to have 128 evaluable women who will have both baseline and 52-week measurements of percent MD of the breast, 64 women in each group.

With 64 women in each group, we will have an 80% power to detect a decrease of percent MD of 6% in treatment group against 2% in placebo group, with a common standard deviation of 8%, using a two-sided t-test with a significance level of 0.05. The proposed difference between the active treatment and placebo groups and the standard deviation are based on conservative estimates from the published work by Cuzick et al. The sample size calculation is performed using nQuery + nTerim 3.0.

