### 13.4 Primary Objective, Endpoint(s), Analysis Plan

The primary objective of this study is to evaluate the change in percent MD (using Cumulus software) from baseline to the week 52 in women applying 4 mg OHT gel versus placebo based on the intent-to-treat principle. The intent-to-treat population is defined as all participants who are randomized and have MD measurements from both baseline and 52 weeks. The primary analysis will be performed comparing the active group versus placebo group per randomization, regardless of the compliance of each participant.

The percent MD is the MD (percent dense area) that is visually estimated using both the mediolateral oblique (MLO) view and the craniocaudal (CC) view as the proportion of the total breast area that was composed of dense tissue (to the nearest 5%). For the study purpose, the densest breast will be the target lesion for the primary endpoint. Breast biopsy for secondary and exploratory endpoints will be performed in the opposite (non-target) breast.

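### The primary endpoint measures the densest breast without exception, so in a woman with one treated or irradiated breast that breast can become the target

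*Combined protocol and SAP*

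**What the plan says.** Two sections define the target breast, and both use density alone. Section 8.1 states: "For the primary endpoint, the densest breast will be used". Section 13.4 states that "the densest breast will be the target lesion for the primary endpoint". Neither gives an exception, and neither says that the choice is made at the baseline reading and then held.

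The eligibility sections admit women whose two breasts have different histories:

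- Section 4.2.4: "Women with unilateral DCIS (with or without radiation therapy) are eligible as long as they have an unaffected breast".
- Section 4.2.5 lists as an exclusion "Prior bilateral breast surgery (mastectomy, segmental mastectomy, or breast augmentation surgery including breast implants or breast reductions". The exclusion is for bilateral surgery, so a woman with one operated or augmented breast can enter.
- Section 4.1.2 accepts dense tissue by BIRADS "classification) in either breast", so the breast that qualifies her need not be the unaffected one.

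Sections 8.2 and 13.4 fix the side of the optional biopsy relative to the target: "Breast biopsy for secondary and exploratory endpoints will be performed in the opposite (non-target) breast".

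**The concern.** Section 4.2.4 makes an unaffected breast a condition of entry after unilateral DCIS, yet the endpoint definition never uses that breast. If the treated breast reads denser, the rule selects it. Its change over 12 months may then reflect earlier surgery or radiation as well as the gel.

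Nothing elsewhere closes the gap. Randomization is stratified by site and density category only (13.2). The named sensitivity analyses concern Month 13-18 timing (13.4), menopausal transition and hormone therapy (13.5), not the history of the target breast. The rationale in section 2.3 cites better outcomes in tamoxifen-treated patients, namely "those whose MD declined in the unaffected breast". That evidence comes from women treated for ER-positive cancer and sets no rule here, but it was gathered on the side that this rule may pass over.

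At stake are the precision and the interpretability of the primary comparison. In women who have the biopsy, density and tissue may also come from breasts with different histories.

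**Working it through.** **1. What the rule does, by type of woman**

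| Woman | Target under 8.1 and 13.4 | Side of optional biopsy |
|---|---|---|
| No prior breast treatment | Denser breast | Other breast |
| Unilateral DCIS, breast conserved, treated side denser | Treated breast | Unaffected breast |
| Unilateral DCIS, breast conserved, unaffected side denser | Unaffected breast | Treated breast |
| Implant, reduction or segmental mastectomy on one side (inferred from 4.2.5) | Whichever is denser | The other |
| Unilateral mastectomy | Remaining breast only | The rule points to the removed side |

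The second row is the clearest problem. The fourth is the same problem, but the documents do not attach an unaffected-breast condition to it.

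**2. The plan's own sample size**

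Section 13.1 states that "we will have an 80% power to detect a decrease of percent MD of 6% in treatment group against 2% in placebo group". Its other inputs are a common SD of 8, a two-sided t-test at 0.05 and 64 evaluable women per arm.

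- Difference: 6 − 2 = 4 points. Standardized: 4 / 8 = 0.5.
- Noncentrality: 0.5 × √(64/2) = 2.83 on 126 degrees of freedom.
- Power: 80.1%. Exact requirement: 63.8, so 64 per arm.
- Attrition: 1 − 128/158 = 19.0%.

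The plan's figures reproduce, with almost no power to spare.

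**3. Effect of treated target breasts**

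Let f be the fraction of evaluable women whose target breast was previously treated. The documents do not give f, so every value of f and every response pattern below is an assumption.

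- No response in those breasts: difference = 4 × (1 − f), SD 8.
- Half response: difference = 4 × (1 − f/2), SD 8.
- Full response, but twice the SD of change: difference 4, SD = √(64(1 − f) + 256f).

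| f | Women of 128 | No response: difference, power | Half response: difference, power | Doubled SD: overall SD, power |
|---|---|---|---|---|
| 0 | 0 | 4.00, 80.1% | 4.00, 80.1% | 8.00, 80.1% |
| 2% | 2.6 | 3.92, 78.5% | 3.96, 79.4% | 8.24, 77.8% |
| 5% | 6.4 | 3.80, 76.0% | 3.90, 78.1% | 8.58, 74.5% |
| 10% | 12.8 | 3.60, 71.4% | 3.80, 76.0% | 9.12, 69.2% |

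These figures are for the t-test on which the sample size rests, not for the Hotelling test planned in 13.4.

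**4. What a given f requires**

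f counts only women in whom the treated side is the denser one. If that happens half the time (assumption), f = 2%, 5% or 10% needs a unilateral history in 4%, 10% or 20% of evaluable women. That is 128 × 0.04 = 5, 128 × 0.10 = 13 or 128 × 0.20 = 26 women.

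**The case against.** The strongest reply is that the causal links are not in the documents. No section says that scar, radiation change or an implant raises a Cumulus reading, or that such a breast fails to respond. The gel goes on both breasts (5.1), and the endpoint is a within-woman change, so a stable scar or implant is present at both readings. This stands. A reader might infer that a treated breast cannot show the drug effect and that its change reflects only its history. The documents do not support that, so non-response is used above only as an assumption.

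Second, the group may be small. Section 4.2.4 also excludes cancer within the last 3 years (whether DCIS counts is not explicit), 4.2.9 limits prior SERM and aromatase-inhibitor use, and a removed breast cannot be the densest. Step 4 shows that f = 10% needs a fairly common history. This also stands. It limits the size of the problem but does not change what the rule selects.

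Third, moving the target to the unaffected side has consequences. Under the present biopsy rule, the optional biopsy would fall on the treated side in every such woman. A woman who qualified only through her treated breast would have a target that is not dense. If both breasts have some history, a rule needing an untreated breast yields no target. The change would also come late (the appendix pages carry Version 20, February 2022), with a statistician who is not blinded (6.9). These points shape the remedy and do not defend the present wording.

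Two further inferences should be resisted. One is that the rule biases the comparison: randomization balances such women on average. The other is that eligibility relies on an unaffected breast throughout: 4.2.4 says so for DCIS and radiation only.

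**Conclusion.** The concern holds as a defect in the definition of the primary endpoint. The rule in 8.1 and 13.4 can select a previously treated or irradiated breast in a woman who was admitted because her other breast is unaffected. The case is firm for unilateral DCIS with or without radiation. For unilateral implants and surgery it rests on the bilateral-only wording of 4.2.5.

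The expected harm is noise or dilution, not a systematic difference between arms, and the planned sample size is not wrong. The loss cannot be fixed from the documents. If 2% to 10% of target breasts are treated and wholly unresponsive, it is about 2 to 9 points of power; with half response it is about 1 to 4 points. At the low end it is negligible. The case for acting is that the rule can be corrected cheaply, and that correcting it after unblinding would be a post-hoc change to the primary endpoint.

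**What to change.** State in 8.1 and 13.4, before unblinding:

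- In a woman with prior unilateral DCIS or radiation, the target is the unaffected breast. By the same logic this applies to a unilateral implant or major breast surgery of the kinds listed in 4.2.5.
- In all other women the target is the denser breast at the baseline reading.
- The same breast is used at Months 12 and 24 (or the later visits under the COVID-19 plan).
- If both breasts have some such history, the densest-breast rule stays and the woman is flagged.

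Add a sensitivity analysis that excludes women with prior unilateral breast treatment. Because the statistician is not blinded, the side should be assigned from baseline readings and breast history by someone without access to allocation.

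The biopsy-side rule in 8.2 and 13.4 and the either-breast criterion in 4.1.2 must be reconciled with this definition. How the biopsy rule is resolved is for the clinical team.

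The cost is a few sentences and one analysis. The Month 12 and Month 24 mammograms are already bilateral (7.4, 7.5), and a densest-breast rule already needs both sides at baseline. Sites must establish DCIS and surgery history to apply 4.2.4 and 4.2.5. Section 7.2 does not name the side of radiation, surgery or implant as a data item, so it should be confirmed that this is recorded. The downside is that in a few women the target will not be the denser breast, or not the breast that qualified them.

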### 8.2 Secondary Endpoints

Note: data from Month 13-18 visit instead of Month 12 visit will be used if participants were seen under the COVID-19 Contingency Plan. If data were not collected at Month 6 under the COVID-19, such

participants will have missing data.

Breast biopsy for secondary and exploratory endpoints will be performed in the opposite (non-target) breast.

8.2.1 We will estimate and compare the percent change in mammographic breast density (using Volpara) from Baseline to Month 12 in women applying 2mg 4-OHT gel per breast versus placebo.

8.2.2 We will estimate and compare the percent change in mammographic breast density (using LIBRA) from Baseline to Month 12 in women applying 2mg 4-OHT gel per breast versus placebo.

8.2.3 We will compare the percentage of women who underwent a change in BIRADS category, comparing pre-and post- treatment measurements, for recipients of 4-OHT gel versus placebo.

8.2.4 We will conduct subgroup analyses including BIRAD category, menopausal status, cup size, and total breast volume.

8.2.5 We will estimate the percentage of women with  $\geq 10\%$  absolute decrease in quantitative mammographic density percentage between baseline and 12 months, comparing between treated group 2mg per breast 4-OHT gel versus placebo based on Cumulus method.

8.2.6 Markers of Toxicity: Baseline, 6 and 12 months BESS questionnaire will be used. Further blood based toxicity markers will be also evaluated at baseline and again at months 6 and 12 (F VIII, vWB factor, SHBG, lipid profile).

8.2.7 Markers of Tamoxifen exposure (in plasma): Plasma measurements of 4-OHT and related metabolite levels and factors related to tamoxifen exposures will be measured at baseline and again at months 6 and 12. (If baseline drug metabolite levels are low; other plasma biomarkers will not be measured at baseline and month 12. Further, the second analysis of 4-OHT and metabolites at 6 and 12 months will also not be performed).

8.2.8 Markers of Tamoxifen exposure (in tissue): Tissue measurements of 4-OHT and related metabolite levels and factors related to tamoxifen exposures will be measured at baseline and again at month 12. (If baseline drug metabolite levels are low; other tissue biomarkers will not be measured at baseline and month 12. Further, the second analysis of 4-OHT and metabolites at 12 months will also not be performed).

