### 13.5 Secondary and Exploratory Objectives, Endpoints, Analysis Plans

Note: data from Month 13-18 visit instead of Month 12 will be used if participants were seen under the COVID-19 Contingency Plan.

The secondary objectives are:

1. To estimate and compare the percent change in mammographic breast density (using Volpara) from Baseline to Month 12 in women applying 2mg 4-OHT gel per breast versus placebo.
2. To estimate and compare the percent change in mammographic breast density (using LIBRA) from Baseline to Month 12 in women applying 2mg 4-OHT gel per breast versus placebo.
3. To compare the percentage of women who underwent a change in BIRADS category, comparing pre-and post- treatment measurements, for recipients of active agent versus placebo.
4. To conduct subgroup analyses including BIRAD category, menopausal status, cup size, and total breast volume.
5. To estimate percentage of women with  $\geq 10\%$  absolute decrease in quantitative mammographic density percentage between baseline and 12 months, comparing between treated group 2mg per breast 4-OHT gel to placebo based on Cumulus method.
6. To describe symptoms assessed by BCPT Eight Symptom Scale (BESS) questionnaire and laboratory toxicity assessment (Factor VIII (F VIII), Von Willebrand (vWB) factor, Sex Hormone-Binding Globulin (SHBG), lipid profile).
7. To evaluate plasma measurements of 4-OHT and related metabolite levels and factors related to tamoxifen exposure.
8. To evaluate tissue measurements of 4-OHT and related metabolite levels and factors related to tamoxifen exposure.

The exploratory objectives are:

1. To compare the Cumulus vs. Volpara vs. LIBRA breast density measurement methods to estimate percent change in mammographic breast density from baseline to Month 12 in women applying 2mg of 4-OHT gel per breast vs. placebo.
2. To perform correlation of drug concentrations in the plasma and the tissue.
3. To evaluate plasma measurements of Insulin-like growth factor (IGF) pathway members, C-reactive protein (CRP), and estradiol.
4. To compare the 2D natural vs. 2D synthetic breast density measurement using the Cumulus method to estimate percent change in mammographic breast density from baseline to Month 12 in women applying 2mg of 4-OHT gel per breast vs. placebo.
5. To evaluate tissue biomarkers (among women undergoing optional pre- and post-treatment biopsies):  
Terminal duct lobular unit (TDLU) Involution  
Collagen structural changes  

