SETER/PR index: estrogen related transcription  
Ki-67, COX-2, p16, CD68.
6. To examine whether any reductions in mammographic density seen after 1 year of 4-OHT vs. placebo gel application persist at 24 months (or longer under the COVID-19 Contingency Plan), one year after gel application has stopped.

All available data will be summarized and analyzed for the secondary analysis. At the end of the study, participant demographic characteristics; the following measurements at baseline and 52 weeks: 1) MD of the breast, 2) tissue biomarkers (among women undergoing optional pre- and post-treatment biopsies: TDLU Involution, Collagen structural changes, SET index, Ki-67, COX-2, p16, CD68, etc.), 3) plasma measurements of parent drug and related metabolite levels and factors related to 4-OHT exposures, such as IGF pathway members, CRP, estradiol, bisphenol and 4-OHT; and the percentage of women with  $\geq 10\%$  absolute decrease in percent MD between baseline and 52 weeks will be summarized using descriptive statistics, such as mean, standard deviation, median and range for continuous variables and frequency/percentage for discrete variables. The difference of continuous variables between baseline and 52 weeks may be compared between two groups using t-test or Wilcoxon rank sum test, whichever is appropriate. Multivariate analogues to the before mentioned univariate tests, such as Hotelling's  $T^2$  test and multivariate multiple regression will be employed when appropriate. Transformation may be performed when necessary to make continuous variables close to normal distribution before evaluating the change of these continuous variables over time between two groups using repeated measures analysis where the intra-participant correlation is taken into consideration, adjusting for other important covariates. In addition, longitudinal data analysis such as the linear mixed effect model will be applied to evaluate the mammogram density change over time. The treatment effect will be evaluated adjusting for other important covariates. The effect of compliance will be evaluated in the per protocol analysis.

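### Items 8.2.7 and 8.2.8 cancel the on-treatment 4-OHT assays when the pre-gel baseline level is low, which is the expected result in essentially every woman

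*Combined protocol and SAP*

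**What the plan says.** Item 8.2.7 opens by stating that plasma 4-OHT, its metabolites and related exposure factors "will be measured at baseline and again at months 6 and 12". The parenthesis that follows sets a condition, "If baseline drug metabolite levels are low; other plasma biomarkers will not be measured at baseline and month 12", and then adds: "Further, the second analysis of 4-OHT and metabolites at 6 and 12 months will also not be performed".

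Item 8.2.8 has the same structure for tissue. Assays are planned at baseline and Month 12, followed by "If baseline drug metabolite levels are low; other tissue biomarkers will not be measured at baseline and month 12" and by the statement that "the second analysis of 4-OHT and metabolites at 12 months will also not be performed".

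The objectives carry no such condition. Sections 1.2 and 13.5 list plasma exposure (secondary 7) and tissue exposure (secondary 8: "To evaluate tissue measurements of 4-OHT and related metabolite levels and factors related to tamoxifen exposure"). Sections 1.3 and 13.5 list the plasma-tissue correlation of drug concentrations (exploratory 2). The analysis text of Section 13.5 summarises "the following measurements at baseline and 52 weeks", and its list includes "plasma measurements of parent drug and related metabolite levels and factors related to 4-OHT exposures".

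Three other places fix what a baseline sample can contain:

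- The schedule of events (7.1.1) and Section 7.2 put the baseline research blood in the prestudy evaluation, ahead of Day 1, when gel starts.
- Footnote i of 7.1.1 and Section 7.2 put the optional biopsy before the start of intervention, with gel at least 24 hours later.
- Exclusion 4.2.9 allows prior SERM or AI use of at most 3 months, and only if at least 12 months earlier.

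**The concern.** The condition is evaluated on a sample that cannot contain study drug, and it decides whether study drug is ever measured. A low baseline level is the normal state of an untreated woman and says nothing about exposure to the gel. The exception therefore swallows the rule that it qualifies.

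At stake are the only direct measurements of drug delivery in the trial. If density does not change, on-treatment concentrations would help to separate poor delivery from lack of effect. The diary and canister weights (Section 5.6) record use but not uptake.

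The same clauses also stop *other* plasma and tissue biomarkers at baseline and Month 12 without naming them. Exploratory 3 (IGF pathway, CRP, research estradiol), exploratory 5 (tissue biomarkers) and the blood toxicity markers of 8.2.6 are therefore possibly affected. On the literal wording, the *other* plasma biomarkers at Month 6 are not cancelled, which would leave Month 6 values without a baseline. Clinical estradiol in premenopausal women (Sections 7.2 and 7.4) lies outside the gate.

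**Working it through.** The plan gives no figure to reproduce. The check follows the rule through and counts what survives.

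**1. Planned drug-level time points.** Plasma: baseline, Month 6, Month 12 (3). Tissue: baseline, Month 12 (2). Total 3 + 2 = 5, of which 2 + 1 = 3 are on treatment.

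**2. Is the trigger met?** Baseline blood and biopsy precede gel (7.1.1, 7.2), and any permitted SERM use ended at least 12 months earlier (4.2.9). Low drug levels at baseline are thus expected in essentially every woman in both arms. This is an inference from the plan's own rules; the plan states no distribution and no cut-off.

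**3. Consequence**, reading *second analysis* as the post-baseline assays:

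| Baseline plasma | Baseline tissue | On-treatment time points kept | Month 12 plasma-tissue pair |
|---|---|---|---|
| low | low | 0 of 3 | no |
| low | not low | 1 of 3 (tissue Month 12) | no |
| not low | low | 2 of 3 (plasma Months 6, 12) | no |
| not low | not low | 3 of 3 | yes |

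The first row is the expected one. Month 12 is the only planned on-treatment pair, so exploratory 2 loses it in every row but the last.

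**4. Scale for plasma.** With 158 women randomized 1:1 (79 per arm) and two on-treatment draws, at most 158 × 2 = 316 assays are planned, 79 × 2 = 158 of them in the active arm. If the rule is applied woman by woman, the number who keep on-treatment plasma data depends on the share with a low baseline, which is an assumption here:

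- 100% low: 0 women.
- 95% low: 158 × 0.05 = 7.9, about 8 women (79 × 0.05 = 3.95, about 4 active).
- 90% low: 158 × 0.10 = 15.8, about 16 women (79 × 0.10 = 7.9, about 8 active).

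**5. Where the texts conflict.** Each parenthesis contradicts the opening sentence of its own item and leaves the matching objectives in Sections 1.2, 1.3 and 13.5 without on-treatment data. The analysis text of Section 13.5 conflicts at one time point only, plasma at 52 weeks. It names neither Month 6 plasma nor tissue drug levels.

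**The case against.** The strongest reply is that this is a drafting slip. The objectives, the blood schedule in Section 10.2 and the laboratory assigned in Section 10.1 for plasma and tissue drug assays all presume on-treatment measurement. That is plausible, but no section redefines the trigger, the same condition appears in both items, and the text as it stands is an instruction not to run assays. A slip of that kind still needs correcting.

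The second reply is that *second analysis* could mean a repeat run, not the post-baseline assays. The ambiguity is real. However, no repeat run is described anywhere, and each item's opening sentence makes baseline the first measurement and the later visits the next. If a repeat run was meant, the wording needs changing all the same.

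A reader might infer three stronger things that the documents do not support:

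- **That the rule contradicts the whole drug-level analysis in Section 13.5.** It does so only for plasma at 52 weeks, and that paragraph opens by referring to available data, which softens even this.
- **That a null density result would be uninterpretable for exposure.** Diary and canister data remain, and Section 13.5 uses compliance as a covariate and in a per-protocol analysis. What is lost is evidence of uptake.
- **That the loss can be sized with the 19% attrition rate or a biopsy count.** The 19% is defined for women with both density measurements, and no biopsy uptake is given. The defect is logical, and such scaling adds nothing to it.

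**Conclusion.** The rule is wrong as written. Followed on its natural reading, it leaves 0 of 3 on-treatment drug time points, so 2 of 8 secondary objectives (7 and 8) and 1 of 6 exploratory objectives (2) have no on-treatment concentrations.

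The count rests on two assumptions: that baseline levels are judged low in essentially all women, and that *second analysis* means the post-baseline assays. The text also leaves open the threshold for *low*, the scope of *other*, and whether the rule applies per woman or to the whole study.

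The primary endpoint, its sample size and secondary objectives 1 to 5 are unaffected. Samples are still scheduled for collection, so the loss is avoidable if the text is corrected before the assays are run.

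**What to change.** Delete the baseline level as the trigger in 8.2.7 and 8.2.8, so that the Month 6 and 12 plasma and Month 12 tissue drug assays are run as each item's opening sentence plans. Reconcile both items with Section 13.5, including Month 6 plasma and the tissue drug levels that its analysis text does not name.

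If the sponsor still wants a cost gate on the other biomarkers, tie it to a prespecified on-treatment level and state the visit, the threshold and the assays covered. Section 6.2 reports that topical 4-OHT gives very little drug in plasma, so a plasma threshold should not be one that this expected finding alone would trip.

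The change is to wording and needs no extra sample collection. The cost is the assays that the literal rule would have cancelled: at most 316 plasma drug assays over both arms, one Month 12 tissue drug assay per biopsied woman, and whichever *other* biomarker assays the gate was meant to cover. The 316 is a ceiling, because the COVID-19 contingency plan already accepts some missing Month 6 blood.
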